#### **4.7 Exploratory Endpoints**

1. GVHD biomarker concentrations (ST2 and REG3) and their associations with clinical endpoints at day 28
2. Patient reported outcomes (QOL) through day 180
3. Linear growth velocity (change in height, relative to sex- and age-means)

#### **5.0 PATIENT ELIGIBILITY**

Subjects must meet all of the inclusion and none of the exclusion criteria to be eligible to participate in the study. Subjects can begin treatment with prednisone 0.5 mg/kg/day (or equivalent) during screening and prior to enrollment. Day 0 is the day an enrolled patient began systemic steroid treatment, even if prior to confirmation of eligibility.

## **5.1 Inclusion Criteria**

- 5.1.1 Newly diagnosed GVHD that meets criteria for Minnesota standard risk (see section 9.0) except isolated skin rash <25% body surface area without other manifestations
- 5.1.2 Ann Arbor 1 GVHD by biomarkers
- 5.1.3 GVHD not previously treated systemically (topical therapies and non-absorbed steroids are allowed)
- 5.1.4 Any donor type, HLA-match, conditioning regimen is acceptable
- 5.1.5 Age 0-21 years at the time of screening
- 5.1.6 Signed and dated written informed consent obtained from patient or legal representative and assent from pediatric patients capable of providing assent

## **5.2 Exclusion Criteria**

- 5.2.1 Patients treated for GVHD with >0.5 mg/kg/day prednisone for any duration or any steroid treatment for GVHD for more than 2 days prior to screening.\*
- 5.2.2 Patients receiving corticosteroids >0.1 mg/kg prednisone (or other steroid equivalent) for any indication within 7 days before the onset of acute GVHD except for adrenal insufficiency, premedication for transfusions/IV medications, or intermittent use for symptom control such as nausea/vomiting
- 5.2.3 Relapsed, progressing, or persistent malignancy or other condition (e.g., known declining donor chimerism) requiring withdrawal of systemic immune suppression or donor leukocyte infusion (DLI)
- 5.2.4 Patients with uncontrolled infection (i.e., progressive symptoms related to infection despite treatment, persistently positive microbiological cultures despite treatment, viral reactivations unresponsive to treatment, or any other evidence of severe infection)
- 5.2.5 Patients requiring mechanical ventilation or cardiac pressor support
- 5.2.6 A clinical presentation resembling de novo chronic GVHD or overlap syndrome developing before or present at the time of enrollment
- 5.2.7 Patients who are pregnant

\*Patients on  $\leq 0.5$  mg/kg/day prednisone for  $\leq 2$  days for new onset GVHD can be eligible as delineated in section 6.0

## **6.0 SUBJECT SCREENING AND REGISTRATION PROCEDURES**

To be eligible for this study, patients must have newly diagnosed low risk acute GVHD defined as Minnesota standard risk based on symptoms and Ann Arbor 1 GVHD based on biomarkers.

Biomarker assays will be performed at the Mount Sinai GVHD laboratory CLIA-certified laboratory according to established protocols. Patients will be recruited from centers participating in the Mount Sinai Acute GVHD International Consortium (MAGIC) where the procedures for obtaining screening samples for biomarker scoring are already established. **Patients can be treated with 0.5 mg/kg/day prednisone (or equivalent) for new onset GVHD for up to 2 days prior to screening**

Consented patients will be registered into the remote data entry system using a unique study number automatically assigned by the database. Five mL of serum will be collected from patients after GVHD has been diagnosed and within 1 day of initiation of treatment. If shipping Monday-Thursday, use the **first overnight** shipping option, or if shipping on Friday, use the **priority overnight for Saturday delivery** shipping option, and send to the Mount Sinai GVHD laboratory for early AM arrival (**see Appendix A for detailed collection and shipping procedures**). Samples can be received Tuesday through Saturday. Once received in the laboratory, the GVHD biomarkers used to assign the Ann Arbor GVHD risk score will be measured by ELISA using standard technical procedures. Processing, measuring, and confirming the ELISA assay results take 4.5 hours (range 4-6 hours). Once the Ann Arbor GVHD risk score is confirmed, the investigator at the participating center will be notified of the score by telephone and written confirmation by email.

Patient registration for this trial will be centrally managed by the MAGIC Data Coordinating Center of the Icahn School of Medicine at Mount Sinai as described below:

[figure not shown]
A potential study subject who has been screened for the trial and who has signed the Informed Consent document will be initially documented by the participating site on the electronic Screening and Enrollment Log provided by the MAGIC Data Coordinating Center (DCC).

It is the responsibility of the local site investigator to confirm patient eligibility for the clinical trial. Confirmation of the MAGIC GVHD risk score will be provided directly to the identified Primary Site contact at the participating site by the MAGIC DCC. All other eligibility criteria will be provided by the participating site. After patient eligibility has been determined, a copy of the **completed** Eligibility form will be submitted by the requesting site to the MAGIC Data Coordinating Center by email to [[contact]](mailto:[contact]) with local site investigator signature and supporting source documentation.

The MAGIC Coordinator, who acts as the registrar, will review the submitted documents and process the registration. An email will be sent by the registrar to the requesting site registrar to confirm patient registration. Patients found to be ineligible for participation after being consented will be considered screen failures, and documented as such in the Screening and Enrollment Log. These patients will not be followed on study.

## **7.0 TREATMENT PLAN**

## 7.1 Treatment Dosage and Administration

**Table 1: Treatment Schema**

TX		Week 1			Week 2			Week 3***	Week 4	Cumulative mg/kg
MAP	mg/kg	MAP	Response	mg/kg	MAP	Response	mg/kg	mg/kg	mg/kg	
AA1	0.5	>0.29	All	1-2**	Ad lib or clinical trial					
			Progression							
		≤0.29	Responder	0.35	≤0.29	Responder	0.25	0.15	0.1	8.75 (↓68%)
						Partial loss of response*	0.35	0.25	0.15	10.9 (↓60%)
						Flare	1-2**	Ad lib or clinical trial		
AA1	0.5	≤0.29	Stable	0.5	>0.29	All				
					≤0.29	Responder	0.35	0.25	0.15	11.2 (↓59%)
						Stable	1-2**	Ad lib or clinical trial		
					>0.29	All				

\* partial loss of response = increase in GVHD stage from week 1 but less than baseline  
 \*\* suggested dose  
 \*\*\* partial loss of response, delay taper, refer to protocol section (section 7.1.9)

- 7.1.1 To avoid delays in treatment and because steroid treatment is the standard of care for GVHD, the starting prednisone dose of 0.5 mg/kg/day (or oral or intravenous equivalent) can start before screening is complete. The initial dose is based on its proven effectiveness as a starting dose for grade II GVHD. Dosing frequency can be daily or in divided doses as per institutional standard. For example, a patient who is diagnosed with Minnesota standard risk GVHD can begin prednisone treatment at 0.5 mg/kg/day pending Ann Arbor score results. If Ann Arbor 2/3 GVHD is confirmed, the patient will not be enrolled on the study, and the prednisone dose should be increased to 1-2 mg/kg/day and further treatment will be at physician discretion. If Ann Arbor 1 GVHD is confirmed, treatment should continue at the initial dose with further dose tapers or increases as specified in **Table 1**. In cases where treatment was not begun during

screening, treatment must begin within one day of confirmation of Ann Arbor 1 GVHD. Day 0 is the day that systemic treatment was begun.

- 7.1.2 Subsequent prednisone doses are determined based on the clinical response and MAPs as in **Table 1**.
- 7.1.3 Prednisone dose or equivalent can be rounded to nearest feasible dose based on formulation, dosing options, and institutional practice.
- 7.1.4 Prednisone dose is based on baseline weight.
- 7.1.5 Patients with an early and sustained response over all four weeks are tapered the most aggressively to 0.1 mg/kg/day by week 4.
- 7.1.6 Prednisone dose remains 0.5 mg/kg/day for patients with stable GVHD and a favorable MAP at the first assessment (week 1) do not taper. Slow responders, i.e., patients with response by week 2, begin the taper at week 2.
- 7.1.7 Patients who do not respond by week 2 are removed from study treatment schedule and it is recommended that the prednisone dose be increased to 1-2 mg/kg/day in order to produce a clinical response.
- 7.1.8 Patients with an initial response at week 1 but a partial loss of response at week 2 (e.g., increase in GVHD staging from week 1 but still improved compared to baseline) do not taper further until staging improves.
- 7.1.9 For patients who have a partial loss of response at week 3, delay taper until further improvement in stage.
- 7.1.10 Patients whose GVHD worsens compared to baseline, fails to improve by week 2, or who develop a MAP >0.29 are removed from study treatment schedule and it is recommended that the prednisone dose be increased to 1-2 mg/kg/day with further tapering per physician judgment.
- 7.1.11 Physicians are permitted to increase steroid dosing whenever deemed in the best interest of the patient. The reason for increasing the steroid dose will be reported.
- 7.1.12 Prednisone dosing will be reported weekly through day 28 and then either weekly or whenever the dose is changed, whichever is less frequent, until study day 90. After week 4 prednisone tapering or dose increases will be determined by the treating physician.
- 7.1.13 To promote adherence to the steroid dosing schedule outlined in **Table 1**, the prednisone dose for the week will be communicated by the MAGIC DCC to the treating physician. For weeks 1 and 2 this communication will occur simultaneously with reporting of the biomarker results.
- 7.1.14 **GVHD Prophylaxis Medications**  
Medications given for GVHD prophylaxis such as cyclosporine, tacrolimus, sirolimus, methotrexate, mycophenolate should be continued at therapeutic doses (according to institutional standards) and adjusted as necessary for renal,

central nervous system (CNS) or other toxicity using institutional guidelines. This study allows for changes in GVHD prophylaxis medication (e.g., replacement of cyclosporine with sirolimus for management of posterior reversible encephalopathy syndrome [PRES]) as per institutional standards. GVHD prophylaxis medications will be tapered according to local institutional tapering practices.

#### **7.1.15 GVHD Topical Treatments**

The preliminary data for this study were generated from patients transplanted at multiple centers with heterogeneous GVHD treatment practices. In order to develop “real world” experience in this study, institutional GVHD treatment practices such as topical steroid therapy for skin or upper GI GVHD are permitted.

#### **7.1.16 Ancillary therapies**

Ancillary/supportive care measures for acute GVHD such as the use of anti-motility agents for diarrhea is allowed at the discretion of the treating physician. Use of ursodiol to prevent/reduce gall bladder sludging or prevent hepatic transplant-related complications is allowed according to institutional guidelines.

#### **7.1.17 Supportive Care Guidelines**

All patients should receive the following:

- Transfusion support per institutional practice
- Anti-infective prophylaxis against viral infections (e.g., herpes virus) is required but institutional dosing and duration practices can be followed.
- Anti-infective prophylaxis against *Pneumocystis jiroveci*, bacterial and fungal infections according to standard institutional guidelines.
- Pre-emptive monitoring and treatment for CMV infections is required but otherwise institutional practice can be followed.

### **7.2 Toxicities and Dosing Delays/Dose Modifications**

Steroid treatment is the standard of care for acute GVHD. The goal of this study is to reduce the toxicities of steroid treatment. Toxicities of steroid treatment that are not captured as study endpoints will be assessed according to the NCI Common Terminology Criteria for Adverse Events (CTCAE), version 5.0 and reported according to the Time and Events Table (Section 6.2).

It is anticipated that prednisone doses not in accordance with **Table 1** may occur. For example, a patient with life-threatening steroid toxicities may require discontinuation of treatment. Prednisone dosing delays and dose modifications that deviate from the prescribed prednisone taper will be monitored and their reasons reported.

### **7.3 Concomitant Medications/Treatments**

Concomitant use of investigational agents is not permitted during the treatment phase of the study without PI approval.

### **7.4 Other Modalities or Procedures**

Patients who have undergone allogeneic HCT are often simultaneously being treated for other conditions and transplant-related complications. Such treatments will be considered distinct from the study treatment.

### **7.5 Duration of Therapy**

The duration of protocol therapy on this study is four weeks. Protocol therapy will end after week 4, if any of the conditions for removal of therapy during the first 4 weeks as defined in section 7.1 are met, or if any of the following criteria apply:

- Inter-current illness that prevents further administration of treatment
- Unacceptable adverse event(s)
- Patient voluntarily withdraws from treatment OR
- General or specific changes in the patient's condition render the patient unacceptable for further treatment in the judgment of the investigator

### **7.6 Off Treatment Criteria**

Patients will be removed from study treatment when any of the criteria listed in Section 7.1 or 7.5 apply. The reason for ending study treatment and the date the patient was removed from treatment will be documented in the study record. All patients who discontinue treatment should continue to comply with protocol specific follow-up procedures and remain On Study as outlined in Section 8.2. The only exception to this requirement is when a subject withdraws consent for all study procedures or dies.

### **7.7 Duration of Follow-Up**

Patients will be followed until 1 year post-enrollment, withdrawal of consent or until death, whichever occurs first. HCT patients are followed closely and frequent clinical evaluations are the norm. While the following outlines the minimum frequency of follow-up evaluations, it is anticipated that the majority of patients will be evaluated more frequently.

During the first 4 weeks of participation, patients will be seen at least weekly for assessment of their GVHD. Patients will also be evaluated at days 42, 56, 90, 180 and 365. Additionally, patients will be evaluated if GVHD flares.

### **7.8 Off Study Criteria**

**Patients can be taken off study at any time at their own request, or they may be withdrawn at the discretion of the investigator for safety, behavioral, or administrative reasons. The reason(s) for discontinuation from study will be documented and may include:**

- 7.8.1 Patient withdraws consent (termination of treatment and follow-up);
- 7.8.2 Loss of ability to freely provide consent through imprisonment or involuntary incarceration for treatment;
- 7.8.3 Patient is unable to comply with protocol requirements;
- 7.8.4 The subject has any disorder or condition that in the investigator's judgment may impede the participant's participation in the study, pose increased risk to the participant, or confound the results of the study
- 7.8.5 Termination of the study;
- 7.8.6 Patient completes protocol treatment and follow-up criteria.

Discontinuation of study treatment (such as subsequent to starting systemic steroids) does not remove the patient from other aspects of study participation including providing follow-up data. Participants will be encouraged to provide this information whether or not they complete the anticipated course of study treatment.

## **7.9 Patient Replacement**

Patients who enroll in the study but (1) do not receive prednisone treatment or (2) initiate prednisone at a dose higher than 0.5 mg/kg (rounding to achieve a feasible dose is allowed) will be replaced. The number of patients and reason(s) for replacement will be reported and will be used to assess the feasibility of the study design. Patients who withdraw consent or are lost to follow-up prior to day 28 will also be replaced. Patients who do not follow the protocol defined steroid dosing will be considered evaluable and not replaced. Reasons for not following the protocol defined steroid dosing will be reported.

## **8.0 STUDY PROCEDURES**

### **8.1 Screening/Baseline Procedures**

Assessments performed exclusively to determine eligibility for this study will be done only after obtaining informed consent. Assessments performed for clinical indications (not exclusively to determine study eligibility) may be used for baseline values even if the studies were done before informed consent was obtained. Frequent monitoring of clinical chemistry and hematology is routine in HCT patients. This study does not require specific laboratory monitoring other than specified below.

#### **8.1.1 Informed consent (and assent from children when applicable)**

#### **8.1.2 Demographics**

#### **8.1.3 Review subject eligibility criteria**

#### **8.1.4 Review concomitant medications** (immunosuppressants and GVHD prophylaxis medications only)

#### **8.1.5 Baseline PRO Assessment**

#### **8.1.6 Adverse event assessment**

Baseline adverse events will be assessed and preexisting conditions will be reported. See Section 10.0 for Adverse Event monitoring and reporting.

#### **8.1.7 Serum chemistries (within 3 days prior to enrollment)**

ALT/SGPT, AST/SGOT, total and direct bilirubin are required for assessment of exclusion criteria within 3 days prior to enrollment.

### **8.2 Follow-Up Procedures**

The following outlines the minimum frequency of follow-up evaluations, it is anticipated that the majority of patients will be evaluated more frequently.

During the first 4 weeks of participation (i.e., through the primary endpoint), patients will be evaluated at least weekly for assessment of their GVHD. Patients will also be evaluated at study

day 42, 56, 90, 180, 1 year and at the time of GVHD flares. Telehealth visits are permitted when in-person visits are not feasible.

Patient compliance with self-administration of prednisone will be assessed by pill diary. Patients will record whether they took their prescribed dose daily for the first 28 days of treatment. Pill diaries will be reviewed at specified study visits and discrepancies with prescribed and actual administration resolved.

PRO tests will be administered at baseline, day 28, day 90 and day 180 visits. Participants will complete the study assessments in-person during their follow-up visits. We will use email, paper copies by US mail, or verbal completion by video or telephone visits when in-person assessment is not feasible. In some cases the baseline PRO will be administered prior to confirming eligibility. If this is the case and patient is a screen fail, the PRO survey will be destroyed. PRO tests are provided in Appendix B.

Infections, as defined in sections 9.1.11 will be closely monitored on this study. In our preliminary data, all patients who developed at least one serious infection did so within 90 days. Given these data, we will monitor for serious infections from start of study treatment through study day 90.

**TABLE 2: TIME AND EVENTS TABLE**

	Screening	Study day 0	Study day 7	Study day 14	Study day 21	Study day 28 	Study day 42	Study day 56	Study day 90	Study day 180	Study day 365	GVHD Flare 
Windows	Newly diagnosed acute GVHD in need of systemic treatment +/- 1 day	Start of prednisone (or equivalent) therapy	+/- 2 days	+/- 2 days	+/- 2 days	+/- 2 day	+/- 3 days	+/- 3 days	+/- 7 days	+/- 14 days	+/- 21 days	+/- 3 days
Eligibility Review	X											
Concomitant Medication Review 	X	X	X	X	X	X	X	X	X			
Steroid Dose Collection	X	Steroid dose will be collected at each study visit during the first 90 days of study and changes occurring outside of the defined timepoints will be captured on an ad hoc form through study day 90										
Adverse Event Evaluations 	X	Adverse events will be reported from study day 0 through day 56. Report serious adverse events as they occur.										
Infections		Infections as defined in sections 9.1.11 will be reported from study day 0 through study day 90										
Serum Chemistry	X											
GVHD Staging 	X	X	X	X	X	X	X	X	X			X
Height and Weight	X					X		X	X	X	X	
Survival, Relapse & Chronic GVHD Status										X	X	
Patient Reported Outcomes		X 				X 			X 	X 		

(PRO) Assessment 												
	CORRELATIVE STUDIES											
5 ml serum 	X		X	X	X	X						X

 The primary endpoint is assessed on day 28 ±2 days

 Concomitant medication review will report **only** immunosuppressants and other drugs administered during the reporting period for GVHD prevention and treatment.

 Serious adverse events are reported as they occur. Other adverse events can be batch reported after day 56 of study.

 GVHD staging will follow the detailed guidelines provided in the MAGIC Acute GVHD Staging Guidance. GVHD staging and treatment should be reported weekly through day 100 post-HCT for patients co-enrolled on the MAGIC natural history study as per the natural history study calendar of events. Steroid dose changes occurring outside of the defined timepoints will be captured on an ad hoc form through study day 90.

 PRO tests consist of 7-10 questions that can be administered within 15-20 minutes. These should be completed during in-person visits. When an in-person follow-up is not available, PROs are permitted to be administered via email, paper copies by US mail, or verbal completion by video or telephone visits. PRO measures are included in Appendix B.

 The windows to administer PROs are 4 days for the baseline, 7 days for the day 28 assessment, 21 days for the day 90 assessment, and 28 days for the day 180 assessment.

 Serum samples will be banked for correlative studies. (For patients co-enrolled on the MAGIC natural history trial: To avoid unnecessary sample collection, when GVHD driven samples are collected within 3 days of a scheduled calendar based sample, the calendar based sample should not be collected).

 Collect GVHD staging data and a serum sample at the time of the first GVHD flare during the follow-up period, if needed

## 9.0 GVHD CLINICAL STAGING

GVHD clinical staging will be according to the established MAGIC criteria.

	Stage 0	Stage 1	Stage 2	Stage 3	Stage 4
Skin	No rash	Rash < 25% BSA	25-50%	> 50% Generalized erythroderma	Plus bullae and desquamation >5% BSA
Liver	Bilirubin ≤ 2 mg/dl	2.1-3 mg/dl	3.1-6mg/dl	6.1-15mg/dl	>15mg/dl
GI tract	Adult: < 500 ml/day Children <10 mg/kg/day	Adult: 500–1000 ml/day Children 10-19.9 mg/kg/day	Adult: 1001-1500 ml/day Children 20- 30 mg/kg/day	Adult: >1500 ml/day Children > 30 mg/kg/day	Severe abdominal pain +/- ileus, frank blood or melena (regardless of stool volume)
UGI		Severe nausea/vomiting			

 
For GI GVHD, children is defined as <18 years of age and <50 kg weight
 
For stage 4 GI GVHD, severe abdominal pain is defined as (1) pain that requires opioid use and (2) pain that significantly impacts on performance status as determined by the treating physician
 
Comprehensive GVHD staging guidance is provided in the MAGIC GVHD Staging Guidance.
 
					

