### **Minnesota Risk Scoring:**

#### **Standard Risk:**

Stage 1-3 skin (single organ system)

Stage 1 GI (single organ system)

Stage 2 lower GI (if upper GI is absent)

Stage 1 upper GI + Stage 1-2 lower GI

Stage 1-3 skin + Stage 1 GI (two organ system involvement)

Stage 1-3 skin + Stage 1-4 liver (two organ system involvement)

**High Risk:** Any other combination of single or dual organ aGVHD stages

**Minnesota risk scoring calculator:** <http://z.umn.edu/MNAcuteGVHDRiskScore>

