## **9.1      Endpoint and Response Criteria**

### **9.1.1      Definitions**

**Treatment Response** is defined as a patient's weekly clinical GVHD response due to systemic treatment, typically systemic steroids, without taking into account if new lines of treatment were given.

**Study Response** is defined as a patient's day 28 clinical GVHD response due to systemic treatment, with also taking into account if new lines of treatment were given.

**Complete Response (CR):** All evaluable organs (skin, liver, GI tract) stage 0. For a response to be scored as CR on day 28, the patient must be in CR on that day and have had no intervening additional GVHD therapy.

**Partial Response (PR):** An improvement in one or more organ involved with GVHD symptoms without worsening in others. For a response to be scored as PR on day 28, the patient must be in PR on that day and have had no intervening additional GVHD therapy.

**Very Good Partial Response (VGPR):** Any response that approximates a CR with the exception of rash <25% body surface area. For a response to be scored as VGPR on day 28, the patient must be in response on day 28 and have had no intervening systemic therapy for acute GVHD other than steroids.

**No response (NR):** All responses that are not CR, PR, or VGPR. Patients who receive any systemic GVHD therapy other than the continuation or modification of GVHD prophylaxis, systemic steroids, and topical/non-absorbable oral steroid therapy, will be scored as NR on day 28 regardless of organ staging.

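### The paediatric GI staging thresholds in section 9.0 are printed in mg/kg/day although the row stages stool volume; the table's own figures point to ml/kg/day

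*Combined protocol and SAP*

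**What the plan says.** In the GI row of the section 9.0 table, each cell from stage 0 to stage 3 gives an adult and a child threshold:

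- Stage 0: adults under 500 ml/day; "Children <10 mg/kg/day"
- Stage 1: adults 500 to 1000 ml/day; "Children 10-19.9 mg/kg/day"
- Stage 2: "Adult: 1001-1500 ml/day Children 20- 30 mg/kg/day"
- Stage 3: "Adult: >1500 ml/day Children > 30 mg/kg/day"

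The stage 4 cell, which rests on pain, ileus or bleeding, sets stool volume aside, so volume is the quantity that the other cells grade. A note under the table restricts the child thresholds to patients under 18 years who weigh under 50 kg.

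Section 9.0 also says that staging follows the established MAGIC criteria and refers to the MAGIC GVHD Staging Guidance for detail. Table 2, footnote 4 (section 8.2) repeats that direction for GVHD staging. The protocol does not reproduce the Guidance.

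**The concern.** A mass per kilogram cannot be the paediatric counterpart of a volume scale at these magnitudes. The same unit appears in all four child cells, each beside a correctly printed adult ml, so a slip in reading the PDF is unlikely.

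These are decision thresholds:

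- **Eligibility.** Criterion 5.1.1 requires Minnesota standard risk and cites section 9.0. The standard-risk list stops at lower GI stage 2; every other combination is high risk.
- **Weekly response.** The response categories that drive Table 1 (section 7.1) depend on changes in stage.
- **Day-28 response.** Under 9.1.1, CR needs "All evaluable organs (skin, liver, GI tract) stage 0", and VGPR is defined by closeness to CR. Both feed the primary endpoint (section 4.4).
- **Safety.** Lack of response by day 28 counts as steroid-refractory GVHD (9.1.3), which is the event in the stopping rule (10.6).

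An error in this row therefore reaches further than an error in background text would.

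**Working it through.** **Inputs.** Child cut-offs of 10, 20 and 30 per kg per day, adult cut-offs of 500, 1000 and 1500 ml/day, and the 50 kg limit all come from the section 9.0 table and its notes. Two inputs are assumptions, because the documents do not give them: stool weighs about 1 g/ml, and body weights run from 3 to 50 kg.

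**Step 1: compare the scales at the 50 kg limit.** Daily cut-off = per-kg cut-off × weight.

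- In ml: 10 × 50 = 500; 20 × 50 = 1000; 30 × 50 = 1500 ml/day. These are the adult cut-offs (adult stage 2 is printed as opening at 1001 ml, a 1 ml difference of notation).
- In reverse: 500/50 = 10; 1000/50 = 20; 1500/50 = 30.
- In mg, as printed: 500, 1000 and 1500 mg/day, that is 0.5, 1.0 and 1.5 g/day.
- Ratio at stage 3: 1500 ml × 1 g/ml = 1500 g; 1500 / 1.5 = 1000. The factor scales in proportion to the assumed density.

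**Step 2: the same cut-offs at other weights.**

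| Weight | Stage 0 below, as printed | Stage 3 above, as printed | Stage 0 below, in ml/kg | Stage 3 above, in ml/kg |
|---|---|---|---|---|
| 3 kg | 0.03 g/day | 0.09 g/day | 30 ml/day | 90 ml/day |
| 10 kg | 0.1 g/day | 0.3 g/day | 100 ml/day | 300 ml/day |
| 20 kg | 0.2 g/day | 0.6 g/day | 200 ml/day | 600 ml/day |
| 30 kg | 0.3 g/day | 0.9 g/day | 300 ml/day | 900 ml/day |
| 50 kg | 0.5 g/day | 1.5 g/day | 500 ml/day | 1500 ml/day |

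As printed, the stage 3 cut-off would jump from 1.5 g/day just below 50 kg to 1500 ml/day at 50 kg. In ml/kg the two scales meet.

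**Step 3: follow a literal reading through the plan.** A 20 kg child passing more than 0.6 g of stool a day is GI stage 3. No standard-risk combination contains that stage, so the child is Minnesota high risk and fails 5.1.1. If the printed cut-offs were instead applied only after enrolment, GI stage 0 would need under 0.2 g/day, so CR would be nearly out of reach. A child held at stage 3 could show no GI improvement by volume.

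**Step 4: sample size.** No staging threshold enters section 14.2. As a check, with n = 50 and success declared at 17 or more, the exact upper-tail probability is 0.0003 at a true rate of 0.14. Power is 0.903 at 0.42. The stated 90% power at a two-sided alpha of 0.001 reproduces and does not depend on this point.

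**The case against.** The strongest reply is that the printed table is not the only authority on staging. Section 9.0 and Table 2, footnote 4 make the MAGIC criteria and Staging Guidance govern. The sites are MAGIC centres, and section 3.7 describes data manager training with testing, guidance embedded in the entry forms and out-of-range alerts. A cut-off below 1 g/day for a 20 kg child is also implausible enough to expose itself. All of this stands as mitigation. It does not make the printed cells right: they are the only paediatric thresholds in the protocol, and they should agree with the sources it cites.

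A reader might infer three stronger things that the documents do not support:

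- **That most children in the trial would be excluded.** This needs a literal reading applied to any stool output. It also concerns only patients under 18 years and under 50 kg; enrolment runs to age 21, no weight distribution is given, and the share staged by these cells is unknown.
- **That a site using another unit is staging outside the protocol.** A site following the MAGIC Guidance is doing what the protocol directs.
- **That the primary endpoint becomes unattainable.** It also counts PR, which does not need GI stage 0. The harms are partly exclusive as well: a child excluded at screening has no day-28 response.

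There is a fair caution about the remedy too. At 1 g/ml the match at 50 kg would fit g/kg/day as well as ml/kg/day. The adult unit and the reference to volume favour ml, but the cited Guidance should settle it.

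**Conclusion.** The unit inconsistency is real and is shown by the table's own figures. All four paediatric GI cells carry a unit that puts their cut-offs about 1000-fold below the adult scale at the 50 kg limit, assuming about 1 g/ml. The ineligibility and the distorted GI response follow only from a literal reading, in patients under 18 years and under 50 kg.

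The practical effect is probably limited, because sites are directed to the MAGIC criteria and Guidance. That judgement assumes that the Guidance carries a coherent unit and that the database was not built from the printed table; neither can be verified from the documents. Correction is still worthwhile, because the row supports eligibility, Table 1 response and day-28 response.

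**What to change.** Reconcile the four paediatric GI cells (stages 0 to 3) in the section 9.0 table with the MAGIC criteria and Staging Guidance that the section cites, and print the unit found there. The table's own figures point to ml/kg/day. Then check that the data entry forms, with their embedded guidance, and the automated response computation described in section 3.7 use the same unit. If either was built from the printed table, review the GI stages already recorded for patients under 18 years and under 50 kg.

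The cost is a short correction in the next amendment and a check of the database. It adds no patients, visits or procedures and leaves the sample size unchanged.
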